2.2 Study Hardware/Software

The study will involve testing a new AID system designed to enable full closed loop control and consisting of the following elements: the diabetes assistant (DiAs) prototyping platform, connected to a Tandem t:AP research insulin pump and a Dexcom G6 CGM, and implementing a new "smaller" coding version of the University of Virginia (UVA) AIDANET algorithm. Upon arrival at the hotel, participants will be taught how to use the Tandem t:AP pump as well as the DiAs system, including stopping the system.

2.3 Timing of Device Use

One-Week Control Period: All participants will collect approximately one week of usual care data to serve as control data for cross-over testing as outlined in Section 6.1. During the control period, participants may use an insulin pump either in manual or automated mode that is capable of being downloaded. Participants will be randomized 1:1 to either conduct the control period before use of the AIDANET system (Group A) or after use of the AIDANET system (Group B).

MiniNET 25-Oct-2024 Page 16 of 60

- 174 *Hotel Period*: Participants will arrive at the hotel prior to dinner on the afternoon of Day 1. They
- will be connected to the Tandem t:AP pump, which will be connected to the DiAs platform. A
- Dexcom G6 CGM may be placed on Day 1 or by the participant prior to Day 1 and will also be
- 177 connected to the DiAs platform. The system will be started in the afternoon/evening with
- 178 AIDANET enabled prior to dinner on Day 1. Participants will be taught how to use the DiAs in
- this configuration. The t:AP pump will be programmed with back up parameters determined by
- the study investigator(s). Once started, the participants will have their glucose values managed
- through use of this system during the hotel and Remote Monitored At-Home periods.
- 182 Remote Monitored At-Home Period: Participants will continue to use the Tandem t:AP pump,
- DiAs platform running the AIDANET smaller network system, and Dexcom G6 CGM for glucose
- 184 control for 7 days/6 nights during this period. At the end of the Remote Monitored At-Home
- period, participants will return to their usual diabetes therapy.

2.4 Meal and Exercise Testing

186

187

188

189

190

191

192

193

194

195

196

197

198

199

200

201202

203204

205

206

207

208

209

2.4.1 Meal Testing

During the supervised house/hotel period, participants will be instructed to eat approximately 3 unannounced meals per full day, with the exception of using their usual insulin-to-carbohydrate ratio with dinner one of the 2 nights. The time of completion for these meals will be recorded by study staff. The % CGM>250 mg/dL for the 4 hours after each meal will be recorded and specifically analyzed along with the CGM area under the curve (AUC) for the post-meal 4-hour period. Participants will be instructed to freely eat unannounced meals during the remotemonitored at-home stage but will not be required to record the timing of the meals. The exception is they will be instructed for 1 full day (from waking through bedtime) to announce usual insulinto-carbohydrate for all ingestions and for another full day to announce when they begin to eat. Participants will be educated to consume their usual diet during both the at-home control period and the Remote Monitored At-Home FCL period.

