All key personnel (all individuals responsible for the design and conduct of this trial) have completed Human Participants Protection Training and Good Clinical Practice Training. Further, I agree to ensure that all staff members involved in the conduct of this study are informed about their obligations in meeting the above commitments.

Investigator's Signature	Date:	/	/	
Investigator's Name:				
Site Name: University of Virginia				

MiniNET 25-Oct-2024 Page 4 of 60

LIST OF ABBREVIATIONS

Abbreviation	Definition
ADA	American Diabetes Association
AE	Adverse Event
AID	Automated insulin delivery
AIDANET	Automated insulin delivery as Adaptive Network
AP	Artificial pancreas
AUC	Area Under the Curve
AYA	Adolescent and Young Adult
BDC	Barbara Davis Center
BG	Blood Glucose (as assessed by a blood glucose meter)
BGM	Blood glucose meter
CGM	Continuous glucose monitor
CSII	Continuous subcutaneous insulin infusion
DiAs	Diabetes Assistant
DKA	Diabetic Ketoacidosis
FCL	Fully closed loop
HbA1c	Hemoglobin A1c
HCL	Hybrid closed loop
JDRF	Juvenile Diabetes Research Foundation
MDI	Multiple daily injections
NAP	Neural network artificial pancreas
SAE	Severe Adverse Event
SG	Sensor Glucose (as assessed by a continuous glucose monitor)
SH	Severe Hypoglycemia
T1D	Type 1 diabetes
TAR	Time above range
TBR	Time below range
TIR	Time in range 70-180 mg/dL

MiniNET_25-Oct-2024 Page 5 of 60

PROTOCOL SUMMARY

Participant Area	Description
Title	Safety and Feasibility Testing of a Smaller Network Version of AIDANET
Investigational Device	AIDANET algorithm as smaller network version with DiAs phone, Tandem t:AP insulin pumps, and Dexcom CGM
Objectives	The primary objective of the project is to demonstrate feasibility and safety of the Automated Insulin Delivery as Adaptive NETwork (AIDANET) system run in a new smaller network version, used in full closed loop (FCL) by adults with T1D.
Study Design	Randomized crossover, device safety/feasibility supervised house/hotel with transition to home use, interventional trial of AIDANET
Number of Sites	1
Endpoint	The primary metric for analysis will be change in mean CGM between the week of the control usual-care period and the one-week Remote Monitored At-Home Full Closed Loop period using AIDANET.
Population	 Key Inclusion Criteria Age 18-60 years at time of consent. Clinical diagnosis of T1D, based on investigator assessment, of at least 1 year duration.
Sample Size	Complete 6 participants

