1.1 Introduction

94

95

121

122

123

124125

126

127128

- 96 A major impediment to maintaining blood glucose (BG) control in Type 1 diabetes (T1D) is missed meal boluses, which has been associated with significantly higher HbA1c levels. While the 97 advent of the artificial pancreas (AP) offers promise of safe reductions in HbA1c, our research 98 group previously found that current AP systems only partly compensate for missed prandial 99 insulin.² We thus designed a new system called Automated Insulin Delivery Adaptive NETwork, 100 101 or AIDANET, to be fully automated, utilizing a Bolus Priming System (BPS) that recognizes meal ingestion and delivers a quick priming dose of insulin prior to extreme blood sugar excursions. 102 103 When used as a fully automated closed loop (FCL) system (without any meal announcements to the controller), this system improves glucose time-in-target range (TIR) 70-180 mg/dL compared 104 to a current commercially available system (Control-IQ). We subsequently incorporated this 105 106 system in a neural net and found this to function as well as the previous model-predictive control algorithm. However, the long-term utility of such a system would have to be via use on an insulin 107 108 pump, requiring a refined "smaller" code set to be able to run on internal pump software.
- 109 We have thus formulated a version of AIDANET that has a smaller coding footprint. The goal of the current project is to assess whether this "smaller" version of AIDANET continues to provide 110 111 safe and effective glycemia management as seen in prior formulations. The current study is a 112 randomized cross-over study comparing participants' usual care with one week at home on 113 AIDANET. The week of control at home will follow a two-night hotel stay when participants will be taught how to operate the new system during the at-home portion of the study. The comparator 114 usual care week will be randomly assigned to being before time on AIDANET (i.e., prior to the 115 116 hotel stay) or after (i.e. time after the one-week home portion).
- For the majority of time on AIDANET, participants will not announce meal ingestion to the system—using the system as an FCL system. However, the system is designed to also be able to be used as a hybrid system with carbohydrate announcement. Thus, as further assessment of the system, we will instruct participants to use the system as follows:

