 - For one of the dinners in the hotel participants will bolus for carbohydrate content of their meal, using their usual insulin-to-carbohydrate ratio (while the other dinner in the hotel will be fully FCL).
 - For one full day while at home participants will bolus for carbohydrates for all ingestions (using their usual insulin-to-carbohydrate ratio).
 - For another full day at home, participants will merely announce to the system each time they begin to eat a meal or snack; this will induce the system to deliver a rapid BPS dose (e.g. 10% of total daily insulin).

We hypothesize that performances of this smaller version of AIDANET will provide safe and effective care when used as FCL (with the exception of the hybrid use as just described). We expect

MiniNET 25-Oct-2024 Page 14 of 60

[figure not shown]
- that this will constitute an important step toward having an AID system that has potential to be
- used embedded in insulin pumps.
- 133 1.2 Study Objective
- 134 This study aims to demonstrate the safety and feasibility of the Automated insulin delivery as
- Adaptive NETwork (AIDANET) system in a smaller software version, used as FCL. This study
- will also assess differences in glycemia outcomes on assigned days when the participant 1) enters
- total carbohydrate amount and 2) announces when food is started to be consumed.
- 138 1.3 Specific Aims and Hypotheses
- 139 Aim 1: To evaluate the performance (safety, efficacy) of the smaller version of AIDANET used
- as FCL.
- 141 **Hypothesis:** FCL use will provide as good or better mean CGM value and glucose TIR during 1
- week of at-home use as compared to 1 week of standard care sensor data.
- 143 Aim 2: To evaluate the safety and efficacy of the smaller version of AIDANET during days where
- participants are assigned to 1) use usual insulin-to-carbohydrate ratio and 2) use meal
- announcement alone (triggering BPS).
- 146 **Hypothesis:** The AIDANET system will yield improved mean CGM glucose and TIR on days
- 147 when meals are announced, both using insulin-to-carbohydrate ratio and simple meal
- 148 announcement.

MiniNET 25-Oct-2024 Page 15 of 60

Chapter 2: Study Synopsis

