1113 14.1 Design and Randomization 1114 The proposed work is a safety and feasibility study of the FCL system and is not intended to be powered to fully demonstrate efficacy of the system. The sample size of up to 6 participants per 1115 session at each site was selected based on previous experience of the feasible number of individuals 1116 1117 to supervise at one time under similar study conditions. 1118 14.1.1 Planned Analysis 1119 The primary outcome of interest will be the change in the mean CGM between the week of the Usual Care observational period and the week of AIDANET at-home. This study represents a 1120 small pilot study to assess the safety and efficacy of the small-version AIDANET system and is 1121 not formally powered. Nevertheless, the randomized crossover design will allow for analysis of 1122 period effects between Group A and Group B. Comparison between these groups will be made to 1123 1124 determine if a period effect can explain part of the benefit of the FCL system during the at-home 1125 period. a. Null Hypothesis: There is no difference in the mean CGM between the week of 1126 Usual Care observational period and the at-home FCL period. 1127 1128 b. Alternative Hypothesis: There is a difference in the mean CGM between the week of Usual Care observational period and the at-home FCL period. 1129 1130 Analysis will involve use of repeated measure ANOVA models to predict CGM average and TIR 1131 with the FCL status a fixed effect and baseline HbA1c and gender as covariates. 1132 Secondary outcomes: 1133 All secondary outcomes will be similarly analyzed. If an outcomes distribution is not suited for mixed model analysis (e.g., profound skewness, or large atom at boundary) we will perform paired 1134 Wilcoxon signed rank test (and loose the capacity to use covariate) to test difference in the median 1135 instead of the mean; this is expected for time below 70mg/dL, number of hypoglycemia, and 1136 1137 possibly time above 250mg/dL. 1138 We do not plan to correct for multiple comparisons. 1139 We do not expect substantial missing values in this supervised study, but if more than 3 participants 1140 have one or more missing admissions, we will consider switching from RANOVA to mixed model repeated measures. 1141 1142 14.2 Sample Size 1143 As an early exploratory study, the goal will be to complete 6 participants to provide data from a

MiniNET 25-Oct-2024 Page 51 of 60

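### Chapter 14 does not carry the two announced-eating days into the at-home analysis, and it gives no analysis for Aim 2

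*Combined protocol and SAP*

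**What the plan says.** **What FCL means.** Section 1.1 introduces the mode with the words "When used as a fully automated closed loop (FCL) system (without any meal announcements to the controller", and says of this trial: "For the majority of time on AIDANET, participants will not announce meal ingestion to the system—using the system as an FCL system". Its closing hypothesis expects safe and "effective care when used as FCL (with the exception of the hybrid use as just described".

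**What is assigned at home.** Section 2.4.1 has participants eat freely without announcing, but "they will be instructed for 1 full day (from waking through bedtime) to announce usual insulinto-carbohydrate for all ingestions and for another full day" to signal when they start to eat. Section 8.1 repeats this as two separate days, one on which announcing food triggers a priming dose and one on the usual carbohydrate ratio.

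**What is promised about those days.** Section 1.2 says that the study "will also assess differences in glycemia outcomes on assigned days when the participant 1) enters" carbohydrate amounts or 2) announces the start of eating. The Aim 2 hypothesis in 1.3 is directional: "The AIDANET system will yield improved mean CGM glucose and TIR on days" with announced meals.

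**What is analysed.** The Protocol Summary defines the endpoint as "change in mean CGM between the week of the control usual-care period and the one-week Remote Monitored At-Home Full Closed Loop period using AIDANET", and 14.3.1 uses the same FCL label. Section 14.1.1 states the primary outcome for "the week of AIDANET at-home", but its null and alternative hypotheses speak of the at-home FCL period. The model there has a fixed effect called FCL status, with HbA1c and gender as covariates, and no term for announcement mode. Section 14.3.3 removes CGM data only around recorded occlusions and after communication loss. Section 14.3.4 requires 80% of the analysis window's readings. The unannounced-meal metrics in 2.4.1, 14.3.2 and Table 2 belong to the hotel stage.

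**The concern.** Aim 1 asks how the smaller AIDANET performs as FCL, which Chapter 1 ties to not announcing meals. Followed as written, Chapter 14 answers with an average over five unannounced and two announced days, and the endpoint definition calls that average FCL.

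Two things are at stake. First, the sponsor itself expects announced days to be better. If so, the mixture makes FCL look better against usual care than unannounced use alone would. Section 14.2 presents the trial as a step towards a larger outpatient efficacy study, and a blended figure is a poor planning value for a system meant to run without announcements. Second, Aim 2 has a hypothesis but no comparison, no comparator days and no summary measure. If these are settled after the data are seen, the choice of days and boundaries can shape the answer.

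**Working it through.** The plan states no figure for the announced share, so there is none to reproduce.

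**1. Days.** Sections 2.3 and 8.1 give 7 days and 6 nights at home, two of them announced: 2/7 = 28.6%.

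**2. Complete days.** Discharge is after breakfast on home Day 1 (7.8) and use ends after lunch on home Day 7 (8.1), so only Days 2–6 are complete: 7 − 2 = 5. An assigned day runs from waking through bedtime, so both should fall among these five. That leaves 5 − 2 = 3 complete unannounced days per person. With 6 completers, Aim 2 has 6 person-days in each announced mode against 6 × 3 = 18 unannounced person-days.

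**3. Share of time.** The endpoint averages over time, so time is the relevant weight. Assumed, not in the documents: home use starts 09:00 and ends 13:00, waking at 07:00, 16 waking hours.
- Home window: 6 × 24 + 4 = 148 h.
- Waking to bedtime: 2 × 16 = 32 h; 32/148 = 21.6%.
- Waking to next waking: 2 × 24 = 48 h; 48/148 = 32.4%.
- With 14 waking hours the lower figure is 28/148 = 18.9%.

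The share is therefore roughly 20–30%.

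**4. Effect on the weekly mean.** Let w be the announced share of time and d the announced-minus-unannounced difference in mean CGM. Then

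whole-week mean − unannounced mean = w × d.

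The same identity holds for TIR, which is a share of time. The documents give no d. For illustration only, if d were −10 mg/dL, the weekly mean would be lower by 0.216 × 10 = 2.2 to 0.324 × 10 = 3.2 mg/dL. If d were zero there would be no shift, and if d were positive the shift would reverse.

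**5. The 80% rule.** With complete CGM data, the time outside the two days is 148 − 32 = 116 h (116/148 = 78.4%) or 148 − 48 = 100 h (100/148 = 67.6%). Both are below 80% of the full home window. An unannounced-only analysis would fail 14.3.4 unless the retained window is the denominator.

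**6. Exclusion boundary.** Take 23:00–07:00 as night, so 6 nights × 8 h = 48 h.

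| Window | Night hours | Overnight share |
|---|---|---|
| Intact home week | 48/148 | 32.4% |
| Excluding waking to bedtime | 48/116 | 41.4% |
| Excluding waking to next waking | 32/100 | 32.0% |
| 7-day control | 56/168 | 33.3% |

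Excluding only waking hours over-represents nights and keeps the night that follows each announced day. Excluding to the next waking avoids both.

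**The case against.** The best defence is that nothing is hidden. Chapters 1, 2 and 8 all state the exception, FCL period also serves as the name of the period in Chapter 8, and 14.1.1 describes the primary outcome without the FCL label. That stands: the gap is that Chapter 14 does not carry the disclosed exception into its endpoint, hypotheses or data rules.

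Several stronger readings are tempting but not supported:
- A reader might infer that no unannounced-only analysis exists anywhere. The hotel stage has post-meal metrics for unannounced meals, so the gap concerns the at-home week.
- A reader might infer that the model codes the whole week as FCL. That is plausible, but 14.1.1 does not define the coding of FCL status.
- A reader might count meals: at three a day, 2 + 5 × 3 + 2 = 19, of which 6 are announced (31.6%). The endpoint averages over time, and announcements also cover snacks, so this is not the right weight.

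It is also fair that the whole week matches the 7-day control better than a reduced window does, that this is an unpowered pilot of six with no efficacy decision rule, and that device data (2.5, 14.3.2) may allow the days to be separated later. The first is a reason to keep the whole-week analysis. The others limit the harm, but they supply neither a prespecified boundary nor an Aim 2 analysis.

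**Conclusion.** The point holds for the at-home week. Two of seven days, roughly 20–30% of home time, are assigned to announced eating. Chapter 14 neither separates them nor analyses them for Aim 2, while the endpoint and hypotheses carry the FCL label. The day count comes from the documents; the time share rests on assumed clock times and on whether the following night is included.

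If Aim 2's hypothesis is true, weekly mean CGM and TIR overstate unannounced FCL performance. A reader might infer that the result is known to favour AIDANET, or that the primary comparison is invalid. The documents support neither: they give no announced-minus-unannounced difference, and the whole-week contrast is a legitimate estimate of use as assigned. The harm is to interpretation and to planning the next study. It should be fixed before analysis.

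**What to change.** 1. In 14.1.1 and 14.3.1, keep the whole-week comparison and label it AIDANET use as assigned: mostly unannounced, with two announced days. Add a prespecified analysis of mean CGM and TIR on at-home time outside those two days, and rest any statement about FCL without announcements on it.
2. Define the exclusion as waking to the next waking, with waking to bedtime as a sensitivity analysis. In 14.3.4, apply the 80% rule to the retained window.
3. For Aim 2, compare each assigned day within person with that person's complete unannounced home days, descriptively.
4. Record the dates of the two assigned days on the case report form.

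The cost is a few sentences in Chapter 14 and two date fields. Device data may already identify the days, but a recorded date makes it certain. The drawback is that the FCL-only analysis uses about two thirds to four fifths of the home hours, so it is less precise and matches the 7-day control less well. Reporting both analyses deals with this.

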2.4.2 Exercise Testing

During the supervised hotel period, participants will engage in mild activity (a walk of approximately 30 minutes) on Day 2. Study staff will set a Temporary Control Rate (TCR) of approximately 50-100% starting up to approximately one hour prior to exercise for approximately 2 hours, actual TCR settings will be tailored to an individual person. Study staff will record the duration, approximate intensity (low, moderate, or high intensity), the TBR <70 mg/dL, TBR <54 mg/dL, and any episodes of Severe Hypoglycemia (SH) during the walk and in the 2 hours after the exercise challenges. Participants will be provided with an exercise monitor (e.g., Fitbit) for use during the control and FCL periods. Participants will be allowed to practice their usual exercise routine during the control and remote-monitored at-home FCL periods with use of the TCR as needed. They will not be required to record exercise events during these periods.

MiniNET 25-Oct-2024 Page 17 of 60

2.5 Study Devices Download Data from the study devices will be captured in real-time by the remote monitoring server for the

- 212 DiAs system. In addition, study devices will be downloaded at the end of the Remote-Monitored
- 213 At-Home FCL period.
- 214 **2.6 Study System Issues**
- 215 If the CGM signal becomes unavailable for more than 20 minutes consecutively, closed loop will
- 216 not operate to automatically adjust insulin delivery. If the CGM is not connected, the system will
- revert to the usual open loop function of the pump and deliver insulin with the pre-programmed
- dosing parameters. Resumption of closed-loop control will occur automatically once the CGM
- signal is again available.
- 220 If the DiAs system is unable to maintain connectivity with the Tandem t:AP pump, the pump will
- automatically revert to the pre-programmed dosing parameters after 30 minutes without any need
- for interaction from the user.

MiniNET 25-Oct-2024 Page 18 of 60

223 Chapter 3: Study Screening

- 224 **VISIT 1**
- 225 3.1 Clinical Site
- The study will be performed at the University of Virginia. Screening procedures will be performed
- either virtually or on site, at a clinical research unit, or at the hotel.
- 228 **3.2** Participant Recruitment and Enrollment
- We will enroll up to 12 participants who have been diagnosed with type 1 diabetes for at least one
- 230 year. This enrollment number accounts for dropouts or screen failures that may occur. The goal is
- 231 to complete a total of approximately 6 participants.
- 232 **3.3** Informed Consent and Authorization Procedures
- 233 Before consent has been obtained, participants will be asked inclusion/exclusion criteria questions
- 234 during pre-screening to determine study eligibility. Before completing any procedures or
- collecting any data that are not part of usual care, written informed consent will be obtained.
- Potential eligibility may be assessed as part of routine care examination.
- 237 A participant is considered enrolled when the informed consent forms have been signed by the
- participant and the study team.
- 239 Consenting procedures and documentation are defined in section 16.3.
- 240 After informed consent has been signed, a potential participant will be evaluated for study
- 241 eligibility through review of medical history, performance of physical exam by a licensed health
- care professional, and other testing as needed per the I/E criteria.
- 243 **3.4 Participant Inclusion Criteria**
- 244 The participants must meet all of the following inclusion criteria in order to be eligible to
- 245 participate in the study.

251

- 1. Age \geq 18.0 and \leq 60 years old at time of consent
- 247 2. Clinical diagnosis, based on investigator assessment, of type 1 diabetes for at least one year
- 249 3. Currently using insulin pump for at least three months; Any pump, either open loop or hybrid closed loop may be used.
 - 4. Currently using insulin for at least six months.
- 5. Willingness to switch to use a commercially approved personal insulin (e.g., lispro or aspart, or biosimilar approved products) within the study pump as directed by the study team.

MiniNET 25-Oct-2024 Page 19 of 60

256

257

258

259260

261262

263

264

265

266

267

268

269

270

271

272

273

274

275

276

277

278

279

286

289

- 6. Currently using a Dexcom G6 or G7 CGM.
 - 7. Has one or more supportive companions knowledgeable about emergency procedures for severe hypoglycemia and able to contact emergency services and study staff that either lives with participant or located within approximately 30 minutes of participant and able to locate participant in the event of an emergency.
 - 8. Participant not currently known to be pregnant or breastfeeding.
 - 9. If participant capable of becoming pregnant, must agree to use a form of contraception to prevent pregnancy while a participant in the study (e.g. hormonal contraception, abstinence from heterosexual intercourse). A negative serum or urine pregnancy test will be required for all females of childbearing potential. Participants who become pregnant will be discontinued from the study. Also, participants who during the study develop and express the intention to become pregnant within the timespan of the study will be discontinued.
 - 10. Willingness to use the study FCL system (CGM, pump, and phone) during the relevant study period.
 - 11. Willingness not to start any new non-insulin glucose-lowering agent during the course of the trial.
 - 12. Willingness to participate in all study procedures including the house/hotel session, exercise challenges (e.g., one hour per day during hotel), and to consume approximately 3 unannounced meals per day during the relevant portion of the supervised hotel session.
 - 13. Access to internet at home and willingness to upload data during the study as needed.
 - 14. Investigator has confidence that the participant can successfully operate all study devices and is capable of adhering to the protocol.
 - 15. Participant is proficient in reading and writing English.

